## **5.6** Rescue Medications & Supportive Care

During Phase A/Year 1, subjects who are on the maximum labeled dose (6 or 8 mg q.d.) or maximum tolerated dose (if lower than maximum dose) of glimepiride/matching placebo for at least two weeks and who meet progressively more stringent glycemic rescue criteria (see Table 6) will receive open-label sitagliptin glycemic rescue medication. Sitagliptin must be initiated at either a scheduled or unscheduled visit at the investigational site, and not by a telephone contact. Immediately prior to initiation of rescue medication (at a scheduled or unscheduled visit), subjects meeting rescue criteria must undergo the Rescue Visit procedures referenced in the Trial Flow Chart - Section 6.0. Do NOT collect A1C if the rescue visit occurs within six weeks after Visit 4/Randomization (Day 1). Subjects rescued during Phase A/Year 1 will not be eligible to enter Phase B/Year 2. During Phase B/Year 2, subjects who are on the maximum labeled dose or maximum tolerated dose of glimepiride/matching placebo for at least two weeks and who have FPG results consistently >200 mg/dL (11.1 mmol/L) or A1C >8.0% (64 mmol/mol) will be discontinued from blinded investigational product (see Section 5.8).

The dose of sitagliptin should be initiated according to the local country label. Subjects who have a prior history of hypersensitivity or intolerance to sitagliptin will be discontinued from blinded investigational product (see Section 5.8).

Subjects requiring sitagliptin rescue medication will continue to receive blinded investigational product.

Table 6 Phase A/Year 1 Glycemic Thresholds

Visit Interval	Glycemic Threshold							
After Visit 4/Randomization (Day 1) through Visit 5/Week 6:	FPG consistently >270 mg/dL (15.0 mmol/L)							
After Visit 5/Week 6 through Visit 6/Week 12: FPG consistently >240 mg/dL (13.3 mmol/L)								
After Visit 6/Week 12 through Visit 8/Week 26:	FPG consistently >200 mg/dL (11.1 mmol/L)							
After Visit 8/Week 26: FPG consistently >200 mg/dL (11.1 mmol/L) or A1C >8.0% (64 mmol/mol)								

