# 8.1.1 Efficacy Analysis

The primary and key secondary endpoints, primary analysis population, and primary analysis method that will be employed for the efficacy analyses are presented in Table 9. To address the primary hypothesis that ertugliflozin is non-inferior to glimepiride in A1C reduction at Week 52, the change from baseline in A1C at Week 52 will be analyzed using a constrained longitudinal data analysis (cLDA) method proposed by Liang and Zeger [15]. The cLDA model will include terms for treatment, time, prior antihyperglycemic medication (monotherapy or dual therapy), baseline eGFR, and the interaction of time by treatment with the restriction of a common baseline mean across treatment groups. An unstructured covariance matrix will be used to model the correlation among repeated measurements. The comparisons of interest will be ertugliflozin 15 mg vs. glimepiride, and ertugliflozin 5 mg vs. glimepiride. The primary hypothesis regarding the non-inferiority of ertugliflozin 15 mg versus glimepiride in decreasing A1C will be assessed using the estimated treatment difference from the cLDA model. If the upper bound of the two-sided 95% confidence interval (CI) for the mean difference between ertugliflozin 15 mg and glimepiride is less than the non-inferiority margin,  $\delta = 0.3\%$ , then ertugliflozin 15 mg will be declared non-inferior to glimepiride in terms of A1C reduction at Week 52. The non-inferiority test for ertugliflozin 5 mg in A1C reduction will use the same approach described above for ertugliflozin 15 mg dose level under the multiplicity control strategy described in Section 8.1.3.

Analyses of the change from baseline in body weight and in systolic blood pressure at Week 52 will be performed using the cLDA model as described above.

The primary analysis time point will be Week 52.

Data obtained after the initiation of rescue therapy or after a subject undergoes bariatric surgery will be censored (i.e., treated as missing) in the analyses of efficacy endpoints to avoid the confounding influences of rescue therapy and bariatric surgery. The primary analysis population for all efficacy analyses will be the Full Analysis Set (FAS), comprised of all subjects who receive at least one dose of study therapy and have at least one measurement of the endpoint of interest (either at baseline or post-randomization).

Table 9 Summary of Analysis Strategy for Key Efficacy Endpoints

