# 8.1.4 Power and Sample Size

The trial will randomize approximately 1230 subjects in a 1:1:1 ratio among the 3 treatment groups. A sample size of 410 per arm will provide 97% power to declare non-inferiority in A1C reduction at Week 52 between a given ertugliflozin dose and glimepiride, using a non-inferiority margin of 0.3%, assuming the true mean difference in A1C is 0%, based on the primary analysis population (FAS). The half-width of the 95% CI is expected to be 0.15%. The probability of meeting the non-inferiority criterion for both ertugliflozin doses in the FAS is 95%. In the secondary analysis population (Per-protocol), the power for declaring non-inferiority is 92% per dose, and 85% for both doses. The above calculations are based on the variability and subject attrition assumptions specified in Section 8.2.6.

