# **8.2.2.1** Efficacy Analysis Populations

The FAS population will be the primary analysis population for all efficacy endpoints.

For analyses that use the cLDA model described in Section 8.2.3.1, the FAS population, defined separately for each analysis endpoint, consists of all randomized subjects who:

- receive at least one dose of study treatment;
- have a baseline measurement or a post-randomization measurement for the analysis endpoint subsequent to at least one dose of study treatment.

For secondary analyses that use the ANCOVA model with last-observation-carried-forward, the FAS population consists of all randomized subjects who took at least one dose of study treatment, and have measurements for the analysis endpoint both at baseline and at one or more post-baseline time points.

A secondary population for analyzing primary and key secondary efficacy endpoints at Week 52 and Week 104 will be the Per-Protocol (PP) population. All randomized subjects who take at least one dose of study medication, with a measurement of the analysis endpoint at both baseline and in the day range for the time point of interest (Week 52 or Week 104), without any of the following protocol deviations will be included in this population.

Protocol/Amendment No.: 002-01

• Drug compliance <75%, using the compliance definition provided in Section 8.2.9.

- Use of prohibited antihyperglycemic medications (found in Section 5.5) for a total of ≥14 days or ≥7 consecutive days after randomization and within 180 days prior to the analysis time point.
- Use of pharmacologic doses of corticosteroids for ≥2 consecutive weeks after randomization and within 180 days prior to the analysis time point
- Incorrect double-blind study medication, or a change in metformin dose, for  $\ge 14$  consecutive days during the last 180 days of the trial period of interest

Protocol deviations are not just a repetition of the exclusion and inclusion criteria in the protocol, but a clinical assessment of deviations from the protocol-specified criteria that will either affect or confound the measures of efficacy. Any patient meeting any of the above criteria during the trial period of interest (Week 0 to Week 52 or Week 0 to Week 104) will be excluded from the per-protocol population for that period.

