The final determination on protocol deviations, and thereby the composition of the PP population, will be made prior to the final unblinding of the database at Week 52 and Week 104 and will be documented in separate memos.

A modified FAS (mFAS) population, defined as all subjects in the FAS who do not have any of the protocol deviations defined above, will be an additional secondary population. Subjects who discontinue prematurely without a protocol deviation will be included in the mFAS. Analyses will be performed in this population only if its size differs from that of the PP population by more than 2% of patients in any arm.

Any substantial differences between conclusions based on the FAS, PP, and (if applicable) mFAS populations will be investigated. The number of subjects included in the FAS, PP, and mFAS populations may vary across endpoints due to the degree of missing data for each endpoint.

Data after the initiation of rescue therapy or after a subject undergoes bariatric surgery will be censored (i.e., treated as missing) from analyses of efficacy endpoints.

The time-to-rescue analysis will be performed in the All-Subjects-Treated population.

For all efficacy analyses, subjects will be counted in the treatment group to which they were randomized, regardless of the treatment received during the course of the trial. Details on the approach to handling missing data are provided in Section 8.2.3, Statistical Methods.

**Protocol/Amendment No.:** 002-01

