
**Protocol/Amendment No.:** 002-01

Although the baseline measurement is included in the response vector, it is independent of treatment, and hence, the baseline means are constrained to be the same for different treatment groups. Of note, in the event that there are no missing data, the estimated treatment difference from the above cLDA model will be identical to that from a traditional longitudinal analysis of covariance (ANCOVA) model which uses the baseline value as a covariate. However, unlike longitudinal ANCOVA, the cLDA model accounts for variability in the baseline values, thus providing more accurate standard errors and CIs for individual treatment effects. Moreover, this model allows the inclusion of subjects who are missing either the baseline or post-baseline measurements, thereby increasing efficiency. An example of SAS implementation code is given in Section 12.8.

All other continuous efficacy endpoints will be analyzed using the above cLDA method described for A1C

An analysis of covariance (ANCOVA) model will be used in the PP population as sensitivity analyses for the primary and key secondary efficacy endpoints at Week 52. The ANCOVA model will include treatment, prior antihyperglycemic medication, baseline eGFR, and baseline value. By definition, there will be no missing outcome data in the PP population.

The ANCOVA model as described above will also be used in the FAS population for the primary and key secondary efficacy endpoints. The last-observation-carried-forward (LOCF) method will be used to impute missing data.

If the size of the mFAS population (described in Section 8.2.2.1) differs from the size of the FAS by >2% in any treatment group, primary and key secondary endpoints will be analyzed in the mFAS population using the same cLDA methodology described for the FAS.

All continuous efficacy endpoints will be summarized and plotted over time by treatment group.

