# 8.2.6 Sample Size and Power Calculations

This trial will randomize approximately 1230 subjects into three treatment groups in a 1:1:1 ratio. A sample size of 410 per arm will be equivalent to an effective sample size of 337 per arm at Week 52 in the power calculation for the primary hypothesis test using the cLDA model in the FAS population. The effective sample size accounts for information loss due to missing data and the correlation among repeated measures, and is derived using the method proposed by Lu, et al. [21] under the assumptions of cumulative attrition rates and covariance matrix at Weeks 6, 12, 18, 26, 39 and 52 specified below. An effective sample size 337 per arm will provide 97% power to declare non-inferiority for a margin=0.3% in A1C reduction at Week 52 assuming the true mean difference in A1C between a given ertugliflozin dose level and glimepiride is 0% ( $\alpha$ =0.05, two-sided test) and the conditional standard deviation is 1.0% (Table 14).

The half-width of the 95% CI is expected to be 0.15%. The power for achieving success for both ertugliflozin doses will be approximately 95%. In the per-protocol population, the expected sample size is approximately 63% of the randomized population (257 subjects per arm).

Table 14 Power to Declare Non-inferiority in A1C at Week 52

		Power		95% CI
Population	N per Arm	Per Comparison	Both Comparisons	Half-width
FAS	337 †	97%	95%	0.15%
PP	257	92%	85%	0.17%

†Effective sample size, accounting for missing data and within-subject correlation of A1C over time. Based on a non-inferiority margin ( $\delta$ ) = 0.3%, true difference = 0%, standard deviation = 1%, and  $\alpha$  = 0.05 (2-sided).

Assumptions for the cumulative attrition rates and correlation matrix at Week 6, 12, 18, 26, 39 and 52 are listed below:

- Cumulative attrition rates at Weeks 6, 12, 18, 26, 39 and 52 are 0.073, 0.091, 0.112, 0.160, 0.210, and 0.312, respectively
- Conditional correlation matrix at Weeks 6, 12, 18, 26, 39 and 52 is

1	0.83	0.71	0.67	0.57	0.57
0.83	1	0.89	0.80	0.68	0.66
0.71	0.89	1	0.90	0.76	0.73
0.67	0.80	0.90	1	0.81	0.77
0.57	0.68	0.76	0.81	1	0.85
0.57	0.66	0.73	0.77	0.85	1

The above assumptions are derived based on data from MK-0431 P024.

Table 15 provides the detectable difference at 90% power for endpoints in the secondary hypotheses in the FAS population.

Protocol/Amendment No.: 002-01

Table 15 Power Calculations for Key Secondary Endpoints in the FAS Population

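### The supportive per-protocol A1C ANCOVA drops subjects rescued earlier for A1C >8.0%, so it leans toward non-inferiority when a dose is truly worse

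*Combined protocol and SAP*

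**What the plan says.** Section 8.2.2.1 makes PP a secondary population for the primary and key secondary endpoints. Membership needs at least one dose, no listed deviation, and a subject "with a measurement of the analysis endpoint at both baseline and in the day range for the time point of interest". The same section adds: "Data after the initiation of rescue therapy or after a subject undergoes bariatric surgery will be censored (i.e., treated as missing". In the mapping table of Section 12.7 the Week 52 window opens at Day 320.

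Table 6 in Section 5.6 sets the rescue threshold after Week 26 as "FPG consistently >200 mg/dL (11.1 mmol/L) or A1C >8.0% (64 mmol/mol", for subjects who have spent at least two weeks on the maximum labeled or tolerated dose of glimepiride or its placebo.

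Section 8.2.3.1 analyses the PP set by ANCOVA with treatment, prior antihyperglycemic medication, baseline eGFR and baseline value, as a sensitivity analysis. It states "By definition, there will be no missing outcome data in the PP population", and Table 11 enters N/A for the missing-data approach.

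Section 8.2.6 gives the PP set a size and its own power: "In the per-protocol population, the expected sample size is approximately 63% of the randomized population (257 subjects per arm", with 92% power per dose and 85% for both in Table 14.

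The modified FAS (mFAS) is the FAS without deviators, analysed by cLDA. Section 8.2.2.1 runs it only if its size differs from the PP set by more than 2% in any arm. Section 8.2.3.1 and the Table 11 footnote run it only if its size differs from the FAS by more than 2%.

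**The concern.** A subject rescued before Day 320 has no usable Week 52 A1C and leaves the PP set without any deviation. After Week 26 one reason for rescue is the endpoint variable itself crossing 8.0%. The PP comparison is therefore made among subjects whose earlier A1C mostly stayed under a common ceiling. If one arm is truly worse, more of its poor responders are cut away and the difference shrinks.

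The Missing Data part of Section 8.2.3.1 treats rescue as MAR because it depends on observed values, and relies on a full-likelihood model. That argument does not extend to an ANCOVA that adjusts only for baseline covariates and discards the A1C that led to rescue. So the PP analysis is biased even under the plan's own missing-data assumption.

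At stake is what agreement between FAS and PP is worth. PP has its own non-inferiority power, and Section 8.2.2.1 promises to investigate substantial differences between populations. A PP estimate pulled toward zero makes agreement easier to reach in the case where a warning is needed.

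**Working it through.** **Inputs from the documents.** Margin 0.3% ("using a non-inferiority margin of 0.3%, assuming the true mean difference in A1C is 0"); the criterion is the upper bound of a two-sided 95% CI, so the nominal one-sided error is 2.5%; "the conditional standard deviation is 1.0% (Table 14"); 410 per arm, effective size 337 in the FAS, 257 in PP; Week 39 to Week 52 correlation 0.85; cumulative attrition 21.0% at Week 39 and 31.2% at Week 52.

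**Step 1: reproduce Table 14.** Power = Φ(0.3/√(2/n) − 1.96); half-width = 1.96√(2/n).
- n = 337: 97.3%, half-width 0.151 (stated 97%, 0.15).
- n = 257: 92.5%, half-width 0.173 (stated 92%, 0.17).

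The effective size recomputed from the stated attrition and correlations is 337.4. The PP row assumes a true difference of 0. There, with the same rescue rule in both arms, selection is symmetric, so the stated power cannot reveal the problem.

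**Step 2: analytic check at a true difference of 0.3%.** Assume everyone above 8.0% at Week 39 is rescued and the true difference is 0.3% at both weeks. Let a be the standardized distance from the glimepiride mean to 8.0%, b = a − 0.3 the same for ertugliflozin, and λ(x) = φ(x)/Φ(x). Among those kept:
- expected difference d = 0.3 − 0.85[λ(b) − λ(a)]
- variance per arm V(x) = 1 − 0.85² + 0.85²[1 − xλ(x) − λ(x)²]
- SE = √{[V(a) + V(b)]/257}
- pass probability = Φ((0.3 − d)/SE − 1.96)

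The assumed rescue rate fixes a. Example at 12.9% in the glimepiride arm: a = 1.131, b = 0.831, λ(a) = 0.242, λ(b) = 0.354. So d = 0.3 − 0.85 × 0.113 = 0.204, SE = 0.0753 and pass probability = 24.6%. At 5% rescue, d = 0.242 and pass = 10.9%. At 2%, d = 0.266 and pass = 6.0%.

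For scale, the plan's attrition implies a loss of (0.312 − 0.210)/(1 − 0.210) = 12.9% between Weeks 39 and 52. The documents do not say how much of that is rescue.

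**Step 3: simulation with partial rescue.** Further assumptions: baseline A1C mean 7.8%, SD 0.6; slope 0.5 on baseline; 21% random attrition by Week 39; 7% deviations; equal chance of rescue in both arms for subjects above 8.0%. With an assumed mean glimepiride fall of 0.7%, over 6000 trials per row:

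| Share of eligible rescued | PP per arm | PP estimate | PP pass | Likelihood pass |
|---|---|---|---|---|
| 0 | 301 | 0.300 | 2.8% | 2.9% |
| 1/4 | 283 | 0.283 | 3.9% | 2.5% |
| 1/2 | 265 | 0.263 | 6.2% | 2.2% |
| 3/4 | 247 | 0.233 | 13.0% | 2.4% |
| all | 229 | 0.188 | 31.0% | 2.9% |

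The planned 257 lies between the one-half and three-quarters rows. With all eligible subjects rescued and assumed mean falls of 1.0%, 1.3% and 1.6%, the PP pass rate is 21.6%, 14.5% and 9.5%. A likelihood analysis that keeps pre-rescue values holds its estimate at about 0.30 throughout.

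**Step 4: would the mFAS analysis run?** Completers number 410 × (1 − 0.312) = 282 per arm against 257 in PP, a gap of 25/410 = 6.1%. If that gap is deviations, mFAS differs from FAS by more than 2%. It differs from PP by more still, since it keeps early discontinuers. Both triggers would probably be met, but they are different rules.

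**The case against.** The strongest reply is that nothing is decided here. A reader might infer that a truly inferior dose would be declared non-inferior too often. The documents do not support that. Sections 8.1.1 and 8.2.3.1 declare non-inferiority from the FAS cLDA interval alone, the PP ANCOVA is marked secondary in Table 11, and it gates nothing in the testing sequence. Nor do the documents call PP co-primary. This stands in full.

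A reader might also infer a fixed inflation factor, such as 2 to 10 times. That does not stand either. The documents give no rescue rate, baseline distribution or mean change, and the factor moves with all three. Rescue also requires two weeks at maximum dose, and a pre-rescue A1C from Day 320 onward still counts as Week 52.

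Other safeguards exist: ANCOVA with LOCF in the FAS, which carries forward the pre-rescue A1C; the time-to-rescue comparison; models with other missing-data distributions, including missing not at random (MNAR); and the mFAS cLDA, which would probably run. The quoted sentence is also literally true, and it does not claim to have dealt with missing data, which the plan covers separately.

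These points limit the harm. They do not remove the direction of the bias or the disagreement between the two mFAS triggers, and they leave Table 14 powering the biased version.

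**Conclusion.** The concern holds for the supportive PP ANCOVA. At a true difference of 0.3% its pass rate exceeds 2.5%: about 3-5% with a quarter of eligible subjects rescued, about 5-13% with half to three-quarters, and about 20% or more with nearly all rescued if the mean glimepiride fall is about 1.0% or less (9.5-14.5% for falls of 1.3-1.6%). With no outcome-dependent rescue it is close to nominal.

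The size rests on the assumptions in the working, including equal rescue in both arms for subjects above 8.0%; rescue triggered by FPG was not modelled. The direction needs only that rescue follows A1C and that one arm is worse. The primary decision is sound on this point. The same selection applies at Week 104, because rescued subjects do not enter Phase B and A1C >8.0% in Year 2 can lead to stopping blinded drug. That comparison is supportive and was not quantified.

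**What to change.** - **Sections 8.2.2.1, 8.2.3.1 and Table 11:** run the mFAS cLDA, using all A1C values up to rescue, unconditionally, and name it the per-protocol check for non-inferiority. Delete both size triggers, which also removes the disagreement between them.
- **Completers' ANCOVA:** keep it if wanted, labelled descriptive and not used to support non-inferiority.
- **Missing-data sentence in Section 8.2.3.1:** say that subjects without a Week 52 value are excluded from this analysis.
- **Table 14:** give the per-protocol row for the cLDA in the mFAS. As a rough guide, if deviations remove the same share of everyone as they appear to remove of completers (257/282 = 0.911), the effective size is 337 × 0.911 = 307 and power is Φ(0.3/√(2/307) − 1.96) = 96%.

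The cost is wording and one recomputed row; no new data, subjects or clinical rules are involved, and the analysis is already planned. The real downside is that the per-protocol check then shares the primary analysis's MAR assumption and is less distinct from it, so the planned MNAR models must carry that part of the sensitivity assessment.

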For the analysis of percentages of subjects at the A1C goals of <7.0% and <6.5% at Week 52, the constrained longitudinal data analysis (cLDA) model that is used for the analysis of A1C will be used to impute the missing data for A1C. Imputations of the missing data will be based on the marginal univariate normal distributions with means equal to the predicted values and variances equal to the squared standard errors for the predicted values from the cLDA model. Ten sets of imputations of each missing value will be constructed from the cLDA model. The seed for the random number generator will be 8835002. Observed data will not be imputed. Subjects will be categorized as at or not at the A1C goals (<7.0% or <6.5%) at Week 52 after imputation. An additional analysis of the percentages of subjects at A1C goals will treat all subjects with missing Week 52 data as not being at goal, regardless of the final observed A1C value.

To estimate the odds ratio, each of the 10 imputed data sets will be analyzed by logistic regression. The logistic regression model will include terms for treatment and baseline A1C. Parameter estimates on log odds ratio will be combined using standard multiple imputation techniques proposed by Rubin [20] to yield an overall estimate of log odds ratio. Log odds ratio will be back transformed into odds ratio for final reporting.

**Protocol/Amendment No.:** 002-01

A time-to-rescue analysis will also be performed. The proportion of subjects rescued in each treatment group will be summarized. Plots of the Kaplan-Meier estimate of the distribution of the time-to-rescue will be provided for each treatment arm and log-rank tests comparing the time-to-rescue distribution of ertugliflozin at a specific dose level versus glimepiride will be conducted. In this analysis, subjects will be censored at the time of discontinuation.

To assess the overall benefit of the trial treatment, the proportion of subjects meeting the composite endpoint of an A1C decrease >0.5% with no AE of symptomatic hypoglycemia and no weight gain by the end of Week 52 will be analyzed using the M&N method in the FAS population for both A1C and body weight at Week 52 [16]. Additionally, the proportion of subjects with an A1C < 7% with no symptomatic hypoglycemia at Week 52 will be analyzed using the same MN method in the FAS population for A1C. For both composite endpoints, missing data will be imputed via the LOCF method.

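### Ten imputations leave avoidable Monte Carlo noise in the supportive A1C-goal analyses; 100 would remove most of it at no cost

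*Combined protocol and SAP*

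**What the plan says.** SAP Section 8.2.3.1 imputes missing A1C from the cLDA model before classifying each subject as at or not at goal. It specifies that "Ten sets of imputations of each missing value will be constructed from the cLDA model" and that "The seed for the random number generator will be 8835002". Each draw is normal around the predicted value, with "variances equal to the squared standard errors for the predicted values from the cLDA model". The completed data sets are then analysed one by one: "The logistic regression model will include terms for treatment and baseline A1C", and the log odds ratios are pooled by Rubin's rules. Table 11 makes multiple imputation the primary approach for these endpoints, with a secondary analysis that counts every missing value as a failure to reach goal. The Week 104 analyses are to be analogous.

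Section 8.2.6 gives the planning assumptions: "Cumulative attrition rates at Weeks 6, 12, 18, 26, 39 and 52 are 0.073, 0.091, 0.112, 0.160, 0.210, and 0.312, respectively". It also states that "A sample size of 410 per arm will be equivalent to an effective sample size of 337 per arm at Week 52". The plan gives no reason for ten imputations and no check on Monte Carlo error.

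**The concern.** A multiple-imputation result depends on the random draws, and that dependence shrinks only as the number of imputations grows. With nearly a third of Week 52 values expected to be missing, ten draws may leave the odds ratio, its confidence interval and its p-value visibly dependent on the seed. Objectives 9 and 17 (A1C goal at Weeks 52 and 104) would then be reported with random error that takes only computing time to remove. A borderline result could land on either side of 0.05 for no reason connected with the trial data.

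**Working it through.** **Inputs from the plan.** 410 per arm; cumulative attrition rising from 0.073 to 0.312; correlations of Week 52 with Weeks 6, 12, 18, 26 and 39 of 0.57, 0.66, 0.73, 0.77 and 0.85; "the conditional standard deviation is 1.0" (in % A1C); ten imputations.

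**Step 1: reproduce the plan's figures.** Summing the information over the dropout patterns with the stated correlation matrix gives an effective sample size of 337.4 per arm (stated: 337). With SE = √(2/337) = 0.0770, the CI half-width is 1.96 × 0.0770 = 0.151 (stated: 0.15). Power is Φ(0.3/0.0770 − 1.96) = 97.3% (stated: 97%). All three agree.

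**Step 2: missing information.** For mean A1C, FMI = 1 − 337/410 = 0.178. It is well below the 31.2% missing share because subjects who leave have informative earlier visits.

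**Step 3: Monte Carlo noise, if draws carry the full prediction variance.** The SD of the pooled Z statistic over seeds is about √(FMI/m), which is also the Monte Carlo SD as a share of the standard error. For a result centred on Z = 1.96, the 95% range is 1.96 ± 1.96 × √(FMI/m):

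| FMI | m | √(FMI/m) | range of Z | range of p |
|---|---|---|---|---|
| 0.178 | 10 | 0.133 | 1.70 to 2.22 | 0.026 to 0.089 |
| 0.178 | 100 | 0.042 | 1.88 to 2.04 | 0.041 to 0.060 |
| 0.10 | 10 | 0.100 | 1.76 to 2.16 | 0.031 to 0.078 |
| 0.10 | 100 | 0.032 | 1.90 to 2.02 | 0.043 to 0.058 |

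**Step 4: simulation of the A1C-goal analysis.** Two arms of 410, the plan's attrition and correlations, imputation given each subject's observed visits, logistic regression on treatment and baseline A1C, and Rubin pooling. Assumptions not in the documents: baseline SD 0.6, slope on baseline 0.5, Week 52 mean 7.2 or 7.5, true difference 0.25 (29% to 48% at goal), and dropout either random or weighted towards high prior A1C. Data sets with a many-imputation p-value of 0.045 to 0.055 were kept (8 to 12 per scenario), and the imputations were redrawn 1,500 times. The table shows the widest 95% range of p across scenarios:

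| Draws and dropout | FMI | m = 10 | m = 50 | m = 100 |
|---|---|---|---|---|
| Full variance, random | 0.174 to 0.179 | 0.024 to 0.105 | 0.036 to 0.070 | 0.039 to 0.063 |
| Full variance, moderate weighting | 0.132 to 0.156 | 0.027 to 0.101 | 0.038 to 0.069 | 0.041 to 0.063 |
| Full variance, strong weighting | 0.092 to 0.133 | 0.028 to 0.093 | 0.038 to 0.066 | 0.041 to 0.061 |
| Variance of predicted mean only (SE assumed 0.06), random | 0.030 | 0.039 to 0.065 | 0.045 to 0.056 | 0.046 to 0.054 |

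With full-variance draws and m = 10, about 42% to 52% of seeds gave p < 0.05 in these borderline data sets.

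**Step 5: average cost.** Relative efficiency of ten imputations is 1/(1 + 0.178/10) = 98%. The variance rises by 1.8% and the standard error by about 0.9%.

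**The case against.** The strongest reply is that nothing rests on this p-value. A1C goal is outside the testing sequence of Section 8.2.5, comparisons there are supportive, and Section 8.2.3 treats such p-values as descriptive. The primary A1C analysis is likelihood-based and imputes nothing, and a seed-free analysis of the goal endpoint is also planned. The seed is pre-specified, so it cannot be chosen after results are seen. Rubin's rules already charge for the finite number of imputations, and efficiency is 98%. All of this stands. It limits the point to reproducibility, but it gives no reason to keep ten: a fixed seed fixes one arbitrary draw and does not reduce its error.

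A second reply also stands in part. The plan does not say whether the prediction variance includes the residual. If it is only the uncertainty of the predicted mean, the range with ten imputations is already about 0.04 to 0.065, and more imputations gain little.

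Three stronger readings are tempting but not supported:

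- **Missing information equals the 31.2% missing share.** That would give 0.021 to 0.107 with ten imputations. The plan's own effective sample size contradicts it.
- **The draws ignore each subject's earlier visits, because the SAP calls the normal distributions marginal.** With full variance this would give missing information of (1.1 × 0.312)/(1 + 1.1 × 0.312) = 0.256 and a range of about 0.024 to 0.097. The text does not say so. It centres draws on predictions from a longitudinal model, and the word may mean only that each value is drawn singly.
- **Week 104 missingness rises because rescued subjects cannot enter Phase B.** Post-rescue efficacy data are already treated as missing (Section 8.2.2.1), so those subjects are already missing at Week 52. The plan gives no Week 104 attrition figure.

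**Conclusion.** The point holds as a cost-free improvement. With full-variance draws and missing information of about 9% to 18%, ten imputations leave Monte Carlo noise of roughly 10% to 13% of the standard error. A p-value near 0.05 can range over about 0.026 to 0.089 (at 18%) or 0.031 to 0.078 (at 10%), and up to about 0.024 to 0.105 in simulation. With 100 imputations it stays within about 0.04 to 0.06.

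The 18% follows from the plan's inputs for mean A1C. The 9% to 18% for A1C goal rests on the assumed means, baseline spread and dropout patterns. The ranges describe a result that is already borderline; a clear result would not change.

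A reader might infer that the A1C-goal analysis is invalid, or that a trial conclusion could turn on the seed. Neither follows: the analysis is nominal and supportive, its seed is fixed, and its pooled variance allows for ten imputations.

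**What to change.** In SAP Section 8.2.3.1, change the number of imputations from 10 to 100 in both places where it appears: where the imputations are constructed and where the imputed data sets are analysed by logistic regression. Keep the pre-specified seed, and state that the same number applies to the analogous Week 104 analysis. This cuts the Monte Carlo SD by a factor of √10, about threefold. The same edit could usefully say whether the draw variance includes the residual, since the size of the gain depends on it. The cost is a small text change and minutes of computing, with no effect on sites, subjects or sample size.
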